### 9 STATISTICAL CONSIDERATIONS

#### 9.1 STATISTICAL HYPOTHESES

- Primary Endpoint(s):

We hypothesize that, compared to participants who receive a RT control intervention, participants who receive IBMT for improving brain outcomes will have improved anterior cingulate cortex/medial prefrontal cortex functional activity after completing the intervention at post-assessment. Alternatively, our null hypothesis is that there will be no difference in the effects of IBMT for improving brain outcomes and those of RT at post-assessment.

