#### 9.2 SAMPLE SIZE DETERMINATION

*Our RCT design is focused on determining if within-person brain changes significantly differ across the intervention groups. All participants in this study will be those who use polysubstance. In prior work involving smokers (N = 27), we detected significant fMRI signal changes in the ACC/mPFC (Cohen's  $d = .90$ ) after 2-wk of IBMT than before IBMT . Compensating for the expected variability of findings in ACC/mPFC activity in polysubstance use, we thus expect a conservative, medium to large (Cohen's  $d = .80$ ) effect (i.e., we expect the effect size between the intervention and control conditions to be 0.80 at post-intervention) based on ours and other studies. However, we may expect polysubstance users to be somewhat more variable. Given the power considerations, we increased our sample size to 35 per group, which will give us 90% power to detect fMRI signal changes evoked by IBMT. The target sample size for the proposed study in the R61 phase (n = 70; 35/condition) is designed to provide sufficient evidence to detect significant brain changes in ATC users following interventions. Given we anticipate up to 20% attrition across the R61 phase of the study, power analysis suggests adequate power.*

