### 9.4.2 ANALYSIS OF THE PRIMARY ENDPOINT(S)

*The primary endpoints are brain assessments and are all repeated measures assessed at baseline and post-intervention. For brain assessment of brain assessment of functional activity, whole-brain analyses of fMRI timeseries during resting state will be calculated and for all endpoints based on standardized processing pipelines of fMRI data using REST software ([www.restfmri.net](http://www.restfmri.net)). After these data preprocessing and calculation, numerical values will be generated for each brain voxel. Next, the effects of intervention (IBMT vs. RT) on primary endpoints will be examined using repeated-measures ANOVA with time x group interaction effect. Threshold-free cluster enhancement approach will be used to identify clusters showing significant effects. Variance and covariance across repeated measures will be calculated as part of the ANOVA. Age and sex will be included as covariates to control for potential confounding effects of age and sex on brain outcomes. Results will be presented as F values for the interaction effect, along with p values to indicate statistical significance. Normality and homogeneity of variance assumptions will be checked using SPSS built-in tools for ANOVA. Multiple comparison corrections will be conducted using FDR correction. Missing data will be handled with case-wise deletion.*

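### The 90% power in Section 9.2 matches a single uncorrected 5% two-sample test and is not established for the TFCE/FDR-corrected whole-brain interaction that Section 9.4.2 makes primary

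*Combined protocol and SAP*

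**What the plan says.** Section 9.2 sets the effect size: "we expect the effect size between the intervention and control conditions to be 0.80 at post-intervention". It then says "we increased our sample size to 35 per group", "which will give us 90% power to detect fMRI signal changes evoked by IBMT", and regards power as adequate after up to 20% attrition. It does not name the test, the significance level, the sidedness, a baseline-post correlation or any multiplicity adjustment. Its starting point is a d of 0.90 in 27 smokers, measured "after 2-wk of IBMT than before IBMT", which is a before-after change within one arm.

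Section 9.4.2 describes the primary analysis. A resting-state fMRI value is produced for each voxel of the whole brain, and the group effect is tested as a time x group interaction in a repeated-measures ANOVA. Then "Threshold-free cluster enhancement approach will be used to identify clusters showing significant effects", and "Multiple comparison corrections will be conducted using FDR correction". The FDR level is not given.

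Sections 3 and 9.1 name the anterior cingulate/medial prefrontal cortex (ACC/mPFC) as the region of interest. Section 9.4.2 does not turn that into a regional mean, a mask or a small-volume correction.

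**The concern.** A power figure belongs to a particular test at a particular threshold. The figure in 9.2 appears to belong to one comparison of one number per participant at 5%. The test in 9.4.2 searches the whole brain and calls a location significant only after correction for that search. Nothing in 9.2 carries the 90% from one to the other.

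This matters because the statement in 9.2 is the only quantitative support for enrolling 70 participants. Section 9.4.1 presents the trial as a first step before full-scale trials in the R33 phase. If the corrected map shows nothing, a reader who relies on 9.2 could take that as a negative result from a trial with 90% power, and the plan does not show that it would be one.

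A secondary question is scale. Section 9.2 places 0.80 at post-intervention, whereas a time x group test concerns change. The two agree only at one value of the baseline-post correlation, which the plan does not state.

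**Working it through.** **Inputs from the documents.** d = 0.80 and 35 per group (9.2); 20% attrition, so 56 of 70 or 28 per group (5.5 and 9.2); whole-brain time x group test with TFCE and FDR (9.4.2).

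**Assumptions.** Alpha is taken as 0.05, because 9.4.2 says only that F values are reported "along with p values to indicate statistical significance". The test is read as two-sided because "our null hypothesis is that there will be no difference in the effects of IBMT" is a null of no difference. Both are inferred.

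**Step 1. Reproduce the 90%.** For a two-sample t-test with n per group, df = 2n − 2 and noncentrality λ = d·√(n/2). Two-sided power is P(|T| > t_crit), with T noncentral t.

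- n = 35: λ = 0.80 × √17.5 = 3.347, df = 68, t_crit = 1.995. Power = 91.0% (normal approximation 91.7%).
- n = 34: 90.2%. n = 33: 89.3%. So 34 per group is the smallest size that reaches 90%.
- One-sided 5%, n = 28: λ = 0.80 × √14 = 2.993. Power = 90.5%, also a match.
- One-sided 5%, n = 35: 95.2%. Two-sided 5%, n = 28: 83.6%. A paired test within IBMT, n = 35: 99.6%. None of these matches.
- Using the source value d = 0.90 with 28 per group, two-sided, gives 91.1%. But 9.2 bases its expectation on 0.80.

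Every matching version is a single uncorrected 5% two-sample test. With d = 0.80 on the tested scale, none leaves a useful margin for correction.

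**Step 2. Illustrate a stricter threshold.** The corrected test needs the FDR level, the spatial extent of the effect, the smoothness of the maps and the baseline-post correlation r. None is given. As a stand-in, let correction act as a smaller per-location alpha. With two time points the interaction is a two-sample test on change, so a post-score d of 0.80 (equal variances, no expected baseline difference) becomes

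d_change = 0.80 / √(2(1 − r)).

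This is 0.80/√1.4 = 0.68 at r = 0.3, 0.80/√1.0 = 0.80 at r = 0.5, and 0.80/√0.6 = 1.03 at r = 0.7.

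Two-sided power at 35 per group (df = 68; t_crit = 1.995, 2.650 and 3.439):

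| r | d_change | λ | alpha 0.05 | alpha 0.01 | alpha 0.001 |
|---|---|---|---|---|---|
| 0.3 | 0.68 | 2.828 | 80% | 57% | 28% |
| 0.5 | 0.80 | 3.347 | 91% | 75% | 47% |
| 0.7 | 1.03 | 4.320 | 99% | 95% | 80% |

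The r = 0.5 row also applies if 0.80 was meant on the change scale from the start.

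**Step 3. Read the table.** Down the alpha 0.05 column, moving to the change scale lowers power below r = 0.5 and raises it above. Across each row, a stricter threshold lowers power, by an amount that depends heavily on r. The table leaves out TFCE, which pools neighbouring voxels and may raise power for an extended cluster. It shows how far the answer depends on unstated inputs; it does not estimate the trial's power.

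**The case against.** The strongest reply is that 9.2 contains no arithmetic error: 35 per group and d = 0.80 do give about 90%. The hypothesis names ACC/mPFC, so the authors may have had one regional test in mind. Section 9.2 opens by asking whether within-person change differs between groups, so 0.80 may already be on the change scale. Section 9.4.7 calls the trial a pilot, and 9.4.1 promises effect sizes as well as p values.

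Much of this stands. The sum is right for the test it fits. The basis of the 90% is inferred, since 9.2 names no test or alpha. The scale point is secondary and can move power either way: at r = 0.7 power is still 95% at alpha 0.01, so the 90% could survive some correction. That would need a correlation and a threshold that 9.2 does not give.

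The reply does not supply the missing link. If one regional test was intended, 9.4.2 does not specify it. Being a pilot does not help either, because 9.2 still claims 90% power.

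A reader might go further and infer that the whole-brain test is underpowered, or that its power is some particular low figure. The documents do not support that: with TFCE pooling and an unknown extent of effect, its power cannot be computed. Nor should one calculate the share of truly affected voxels that FDR would detect and call it power. Many affected voxels can be missed while the effect is still found somewhere.

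**Conclusion.** The point holds in this form: the 90% is not established for the primary test that 9.4.2 specifies. With d = 0.80 on the tested scale, it is reproduced only as a single uncorrected 5% two-sample test (91.0% two-sided at 35 per group, or 90.5% one-sided at 28). Alpha and sidedness are inferred, but both matching versions lead to the same conclusion.

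The size of the gap is unknown. Under the per-location stand-in, 35 per group gives anything from 28% to 95% across r = 0.3 to 0.7 and alpha 0.01 to 0.001. That range shows that 90% has not been demonstrated; it does not show that true power is low. Attrition is a separate matter and is not needed for this conclusion.

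This should be corrected, because the figure is the plan's only numerical justification for 70 participants.

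**What to change.** Make the power statement and the primary test refer to the same thing, in one of two ways.

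1. **Preferred.** In 9.4.2, prespecify one ACC/mPFC change value per participant (measure, region definition and summary) as the single primary test, with a two-sided 5% level, and make the whole-brain TFCE/FDR map supportive. Reword 9.2 along these lines: *35 analysed per group gives 91% power for a single two-sided 5% test of one prespecified ACC/mPFC change value with d = 0.80 on the change scale, assuming a baseline-post correlation of [value]; no power is claimed for the TFCE/FDR-corrected whole-brain search.* If the figure is quoted for the 28 per group expected to complete, the same test gives 84%.

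2. **If the whole-brain test stays primary.** Replace 90% with simulated power at the planned TFCE/FDR threshold. State the FDR level, effect extent, smoothness, baseline-post correlation and number analysed, and show a range for each assumed value.

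The protocol should not say that whole-brain power is lower, since that has not been shown.

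The first option costs wording in 9.2 and 9.4.2 and a region definition fixed before analysis; the planned enrolment of 70 need not change. The second costs a short simulation, and whether 70 participants suffice would then depend on its result.

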#### 9.3 POPULATIONS FOR ANALYSES

*The analysis population will be Modified Intention-to-Treat Analysis Population. Specifically, these participants are those who completed the full-dose of the intervention (10 sessions) and have completed data for the primary endpoint.*

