#### 4.4 END-OF-STUDY DEFINITION

A participant is considered to have completed the study if he or she has completed the baseline assessment, 10 intervention sessions, and post-intervention assessment.

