## 5.5 STRATEGIES FOR RECRUITMENT AND RETENTION

*We anticipate to enroll 70 participants (males and females) who are at least 18 years old across different race and ethnicity based on local demographic characteristics. Subjects will be recruited through print and media ads within local community. This will include radio and online ads and recruitment through social media. Flyers will be distributed throughout the local community. Based on our and other's previous experiences in longitudinal studies, about 5-10% of participants will dropout over the study period due to illness or relocation. We plan a dropout rate of 20% for this brief intervention given the population is polysubstance users. We propose to recruit 70 adults of which 56 (80%) will complete the study.*

*Compensation and Retention. Participants will be financially compensated with \$300 in total for completing the study protocol (approximately for 15 hours of time); participants who only partially complete the protocol will be compensated based on prorated hours. To maximize participant retention we will maintain contact with participants over time via frequent assessment intervals (e.g., requiring a functioning phone number and email address to contact participants by phone or email as needed, and obtaining the name, address, and phone number of at least 2 friends or classmates who can provide contact information for the participants, should we be unable to contact them during the study; emails and reminder phone calls prior to all study visits; offer flexible scheduling options for assessment (including weekends); provide fair compensation to participants; and maintain positive relations with participants. These procedures were used to maintain adequate participant retention in our prior NIH studies.*

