## 7 STUDY INTERVENTION/EXPERIMENTAL MANIPULATION DISCONTINUATION AND PARTICIPANT DISCONTINUATION/WITHDRAWAL

### 7.1 DISCONTINUATION OF STUDY INTERVENTION/EXPERIMENTAL MANIPULATION

If a clinically significant finding is identified (including, but not limited to changes from baseline) after enrollment, the investigator or qualified designee will determine if any change in participant management is needed. Any new clinically relevant finding will be reported as an adverse event (AE).

The data to be collected at the time of study intervention discontinuation will include the following:

- The reason(s) for discontinuing the participant from the intervention, and methods for determining the need to discontinue
- If the participant is due to complete assessments within 1 weeks of being discontinued from the study intervention, those assessments will be administered at the time of discontinuation; if the next scheduled assessments are more than 1 week from the discontinuation date, the next scheduled assessment will not be administered. Thereafter, the participant will be not included in all future scheduled assessments, as they did not participate in the intervention.

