### 7.2 PARTICIPANT DISCONTINUATION/WITHDRAWAL FROM THE STUDY

Participants are free to withdraw from participation in the study at any time upon request.

An investigator may discontinue a participant from the study for the following reasons:

- Significant study intervention non-compliance, unless varying compliance is an aspect of the study objectives
- Lost-to-follow up; unable to contact subject (see **Section 7.3, Lost to Follow-Up**)
- Any event or medical condition or situation occurs such that continued collection of follow-up study data would not be in the best interest of the participant or might require an additional treatment that would confound the interpretation of the study
- The participant meets an exclusion criterion (either newly developed or not previously recognized) that precludes further study participation

The reason for participant discontinuation or withdrawal from the study will be recorded. Subjects who sign the informed consent form and are randomized but do not receive the study intervention may be replaced. Subjects who sign the informed consent form, and are randomized and receive the study intervention, and subsequently withdraw, or are discontinued from the study, will not be replaced.

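### The set that section 9.3 calls modified intention-to-treat is a 10-session completer (per-protocol) set, and no as-assigned analysis is defined

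*Combined protocol and SAP*

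**What the plan says.** Section 9.3 defines a single population under the modified intention-to-treat label and limits it as follows: "these participants are those who completed the full-dose of the intervention (10 sessions) and have completed data for the primary endpoint". Section 6.1.2 sets full dose at all 10 sessions, with no lower threshold. Section 4.4 counts a participant as having completed the study who "has completed the baseline assessment, 10 intervention sessions, and post-intervention assessment".

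No other analysis set appears. ITT occurs otherwise only in the abbreviation list (10.3). Section 9.4.2 deletes cases with missing data and names no sensitivity analysis, and 9.4.9 (exploratory analyses) is marked not applicable.

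Other sections decide who could have a post-intervention scan:

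- **7.1:** after discontinuation of the intervention, assessments due within a week are brought forward ("those assessments will be administered at the time of discontinuation"). Otherwise, "if the next scheduled assessments are more than 1 week from the discontinuation date, the next scheduled assessment will not be administered".
- **7.2:** the investigator may end participation for "Significant study intervention non-compliance, unless varying compliance is an aspect of the study objectives", among other grounds. It also provides that "Subjects who sign the informed consent form and are randomized but do not receive the study intervention may be replaced".
- **7.3:** the site tries to reschedule a missed visit within 1 week.
- **4.1:** randomisation takes place before the baseline assessment.

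On expected losses, 5.5 states: "We propose to recruit 70 adults of which 56 (80%) will complete the study". Section 9.2 treats 20% as an upper figure for attrition.

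**The concern.** A modified intention-to-treat set normally keeps nearly everyone randomised, in the arm assigned. Here membership depends on what participants did after randomisation. The arms are still compared as assigned, but only among those who attended every session and supplied complete data. Randomisation protects a comparison of everyone allocated. It does not by itself protect a comparison of completers.

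Two things are at stake. First, a completer result would be reported under an ITT-type name. Second, nobody could tell from the planned analyses whether the restriction mattered, because there is no second analysis to set beside it. Participants with usable data at both time points and fewer than 10 sessions would be left out by rule, not because anything is missing.

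**Working it through.** **1. Label against definition.** The conditions in 9.3 are 10 of 10 sessions and complete primary endpoint data. The conditions in 4.4 are the baseline assessment, 10 sessions and the post-intervention assessment. The primary endpoint (section 3) needs both assessments, so the two definitions select essentially the same people.

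**2. How many are outside the set.** From 5.5, 70 x 0.80 = 56 complete, or 28 per arm if losses are equal. That leaves 70 - 56 = 14, or 7 per arm. The documents do not say how many of the 14 would have both scans. Two rules keep that number down:

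- Rescheduling under 7.3 means that a missed session need not leave someone short of 10.
- Under 7.1, with Visit 12 on Day 31 ±2 (section 1.3), someone who discontinues before about Day 31 - 7 = Day 24 (Day 22 to 26 across the window) gets no post-intervention scan.

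Those who stop later are scanned at discontinuation. Those who miss sessions without being discontinued are still due a scan, unless 7.2 is applied.

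**3. When the completer comparison is biased.** Suppose there is no true effect and completion depends on a trait. Let m be the mean trait among completers in SD units, and let r0 and r1 be the trait's correlations with the baseline and post-intervention values. Selection shifts mean change in an arm by (r1 - r0) x m. The bias is the difference between arms in that shift, divided by the SD of change.

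It is zero if selection and loss are the same in both arms, or if r1 = r0. It is non-zero if r1 - r0 differs by arm, or if it is non-zero and completion rates differ.

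The examples below assume a scan-rescan correlation of 0.6, so the SD of change is sqrt(2 x 0.4) = 0.894. They use m = 0.350, 0.497 and 0.195 for 80%, 70% and 90% completion:

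- Equal selection and loss in both arms: 0.
- r0 = 0.2, r1 = 0.5 in both arms, completion 70% vs 90%: 0.3 x (0.497 - 0.195)/0.894 = 0.10 SD.
- r0 = 0.2, r1 = 0.5 in IBMT only, 80% completing: 0.3 x 0.350/0.894 = 0.12 SD.
- The same with r0 = 0: 0.5 x 0.350/0.894 = 0.20 SD.

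None of these correlations comes from the documents. The list shows when bias arises and that its size follows the assumption chosen. It is not an estimate, and 0.20 is not an upper bound.

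**4. What the as-assigned analysis does to power.** The inputs are d = 0.80 and 35 per group (9.2). Two-sided 0.05 is assumed, because 9.2 states no alpha. The calculation is a two-sample t-test on one value; TFCE and FDR are not modelled.

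- The plan's own figure, 35 per arm at d = 0.80: 91.0%, which reproduces the stated 90%.
- Completers only, 28 per arm at d = 0.80: 83.6%.
- All 35 per arm scanned, with non-completers keeping a share g of the effect: d = 0.80 x (0.8 + 0.2g).

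| Share g kept | d | Power |
|---|---|---|
| none | 0.64 | 75.2% |
| half | 0.72 | 84.4% |
| all | 0.80 | 91.0% |

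If g = 0, mixing responders and non-responders also widens the spread. The IBMT variance becomes 1 + 0.8 x 0.2 x 0.80² = 1.102, the pooled SD is sqrt((1 + 1.102)/2) = 1.025, d = 0.64/1.025 = 0.624, and power is 73.0%. Without that extra spread, the as-assigned analysis matches 83.6% once non-completers keep about 46% of the effect.

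**The case against.** Five points can be made for the plan.

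- **Nothing is concealed.** The sentence after the label says exactly who is included. That is true, and it makes the label a wording error, but it does not supply the missing as-assigned analysis.
- **A full-dose question is legitimate.** Section 9.1 asks about activity after completing the intervention, and 9.4.1 describes an early look at effects and mechanisms before larger trials. This stands, and it is why the completer analysis should be kept. It does not justify having no other analysis: 4.1 describes a randomised trial, the null in 9.1 compares the effects of the two interventions, and the documents offer no mechanistic reason for the restriction in 9.3.
- **Few people may be affected.** Rescheduling under 7.3 and the scan rule in 7.1 may leave only a handful with both scans and fewer than 10 sessions. The 20% is also a planning allowance above the 5-10% that 5.5 reports from experience. This stands and limits the practical size.
- **No harm is shown.** A reader might infer that the restriction will bias the result or inflate type I error. The documents do not support that. They give no evidence that selection differs by arm, the dropout causes that 5.5 names are illness and relocation, and similar group formats (6.1) and participants not knowing which intervention is experimental (6.3) reduce the risk.
- **The alternative set is not full intention-to-treat either.** It still requires a post-intervention scan and, because 4.1 randomises before baseline, a baseline scan. This stands, and the plan should say so.

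**Conclusion.** The point holds as one of labelling and of a missing analysis. Section 9.3 defines a per-protocol set under a modified intention-to-treat name, and no as-assigned analysis exists to set beside it. This should be fixed.

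Up to 14 of 70 participants fall outside the set on the planned allowance. The number who would be dropped with both scans in hand is not given and may be small. Any bias is conditional on selection or loss differing by arm in the ways shown, and its size is unknown.

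A reader might also infer that all 14 have usable data that are being thrown away. Section 7.1 rules that out, since those who discontinue early are not scanned. The power figures rest on d = 0.80, an assumed two-sided 0.05, equal loss by arm and a single ACC/mPFC value, not on the planned voxelwise test.

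**What to change.** **In 9.3:**

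- Relabel the 10-session set per-protocol.
- Add, as the main between-arm comparison, an as-assigned analysis of all randomised participants with usable baseline and post-intervention scans, whatever their attendance.
- Keep the per-protocol analysis beside it as the answer to the 9.1 question about activity after completing the intervention. Attendance is already recorded under 6.4.
- State that the as-assigned set still depends on having a post-intervention scan, and say how scans brought forward under 7.1 are treated.

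**In reporting:** account for every randomised participant by arm, sessions attended and scan status, including those replaced under 7.2 and those randomised without a baseline scan.

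**In 9.4.2:** add a sensitivity analysis on the ACC/mPFC region value, by a likelihood-based model or multiple imputation. The voxelwise pipeline can stay as it is.

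**Separately:** the 7.1 and 7.2 rules on assessment after discontinuation limit how full the as-assigned set can be, and should be reconciled with it. The 9.3 change stands without that. It then adds only those scanned with fewer than 10 sessions.

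**Cost:** wording, a little extra analysis, and possible dilution of the effect. In the worst case calculated, with every non-completer scanned and gaining nothing, power is 73% to 75% against 83.6% for completers. If assessment after stopping were also continued, extra scans could reach about 14 at Visit 12 and as many again at Visit 13, all within the planned 70 participants.
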